## 1. LIST OF ABBREVIATIONS

Abbreviation	Definition
AE	Adverse Event
SAE	Serious Adverse Event
CRF	Case Report Form
eCRF	Electronic Case Report Form
CDC	Clinical Data Coordinator
DC	Data Coordinator
DCF	Data Clarification Form
DMPA	Depot Medroxyprogesterone Acetate
DVP	Data Validation Plan
EIU	Exposure in Utero
IRB/IEC	Institutional Review Board/Independent Ethics Committee
LSLV	Last Subject Last Visit
MFDS	Ministry of Food and Drug Safety
NA	Not Applicable
ODC	Obvious Data Correction
PV	Pharmacovigilance
SAP	Statistical Analysis Plan

### 3. AMENDMENTS AND UPDATES

Document	Version Date	Substantial amendment or Administrative amendment	Summary of Changes
Original protocol	24 May 2013	N/A	N/A
Amendment 1	22 July 2013	Substantial	
Responsible parties amended:
 
1. PPD
 
Amendment due to regulatory requirements:
 

Section 8.2.1. Inclusion Criteria: Women subjects who are currently being treated with Sayana® has been omitted.

Section 8.3.1.1. General Information: Addition of date of contract.

Section 8.3.1.2. Demographic information: “Classification” has been deleted.

Section 8.7.2. Statistical Consideration: Use of 95% confidence intervals has been added where necessary.

Section 8.7.2.1. Safety Analysis & 8.7.2.2. Effectiveness Analysis: Statistical method has been added or modified.

 
Others:
 

Section 8.1.2. Effectiveness endpoint amended: “treatment failure cumulative pregnancy” amended to “cumulative percent of patients who become pregnant by month 6 and rate of pregnancies per 100 person-years of follow-up.”

Section 8.1.2. Method of effectiveness endpoint (endometriosis pain management) measurement amended to visual analogue scale.

Amendment 2	06 Dec 2013	Substantial	
Responsible parties amended:
 
1. PPD
 
Amendment for clarification.
 

Section 8.3.1.2. Demographic information: Collection of method for pregnancy test, purpose of administration and VAS at Baseline have been added.

Section 10.1.5. SERIOUS ADVERSE EVENTS: The meaning of ‘Transmission’

Document	Version Date	Substantial amendment or Administrative amendment	Summary of Changes
			
has been clarified.
 
3. Section 8.7.1.2. Safety Parameters: Additional instruction was added.
 
Amendment due to SOP requirement:
 
 
1. Section 10.1.3. DEFINITION OF AN ADVERSE EVENT: The detail to report overdose, misuse, extravasation associated with the use of a Pfizer product has been added.
 
2. Section 11. PLANS FOR DISSEMINATING AND COMMUNICATING STUDY RESULTS: It has been amended per SOP.
 
3. Section 10.1.1.5: Lack of efficacy reporting requirement was changed.
 
 
Others:
 
 
1. Section 5. MILESTONE: Typo correction.
 
2. Section 8.2. Setting: Correction per local regulation
 
3. Section 8.3.1.1. General Information: “Initial of subject”, which would not be collected, has been deleted.
 
4. Section 8.3.1.4. Concomitant Medication/Therapy: Typo correction.
 
5. Section 8.3.1.5 Administrative Status for Sayana®: CRF change was applied.
 

Amendment 3	26 Mar 2015	Substantial	
Amended per SOP;
 
 
1. Section 10. Averse Event Reporting: Amended with Safety Reporting Language (effective date: 31 Dec 2013) SOP Update.
 

Amendment 4	08 Jul 2016	Substantial	
Amended the total target enrollment number in accordance with MFDS Appeal Letter.
 
Terms revision; Korean term of “Adverse Event” is changed in accordance with updated MFDS Re-Examination Guideline.
 
Others:
 
 
1. “Table of Contents” number correction.
 

Amendment 5	24 Aug 2016	Substantial	Amended the total target enrollment number to submit the complemented document for Appeal letter to MFDS.
Amendment 6	21 Feb 2017	Substantial	
 
1. Section 5. RATIONALE AND BACKGROUND & Section 7.5. Study size: Amended target enrollment number to initial number
 

Document	Version Date	Substantial amendment or Administrative amendment	Summary of Changes
			
2. Section 7.2. Setting: Amended the subject enrollment method from continuous registration method to whole case enrollment method.
 
3. 7.2.1 Inclusion criteria: Amended the subject enrollment criteria (After the site initiation, women subjects who are/were in treatment with Sayana® as per the local product document for usage).

Amendment 7	30 Jan 2018	Substantial	
Author change: PPD PPD
 
RESPONSIBLE PARTIES addition: PPD PPD
 
Protocol amendment
 
1. Section 5. RATIONALE AND BACKGROUND & Section 7.5. Study size: Amended target enrollment number for supplementation document submission to MFDS
 
2. Section 7.2. Setting: Amended the subject enrollment method from whole case enrollment method to continuous registration method.
 
3. 7.2.1 Inclusion criteria: Amended the subject enrollment criteria
 
4. Protocol template change

Amendment 8	21 Mar 2018	Substantial	
Section 4. MILESTONES: Amended milestones of Interim reports & Final study report in accordance with study period extension.
 
Section 5. RATIONALE AND BACKGROUND & Section 7.5. Study size: Amended target enrollment number to initial number in accordance with re-examination period extension.

#### 4. MILESTONES

Milestone	Planned date
Start of data collection	01 April 2014
End of data collection	28 January 2019
Interim report 1 -1	29 July 2013~28 September 2013
Interim report 1-2	29 January 2014~28 March 2014
Interim report 2-1	29 July 2014~28 September 2014
Interim report 2-2	29 January 2015~28 March 2015
Interim report 3	29 January 2016~28 March 2016
Interim report 4	29 January 2017~28 March 2017
Interim report 5	29 January 2018~28 March 2018
Re-Examination application report	29 January 2019~28 April 2019
Interim report 7	29 January 2020~28 March 2020
Final Study Report (8)	29 January 2021~28 April 2021
Product Market Launching	01 July 2013

#### 5. RATIONALE AND BACKGROUND

In light of the number of unplanned pregnancies, women recognize the need for contraception and family planning. In addition to controlling the size of their families, couples also want to control the timing and spacing of births. Moreover, the job of family planning will never be finished. With each new generation, comes a new set of parameters affecting use of contraception.

Barriers to using contraception include worries about side effects, health concerns, social disapproval or partner's opposition, financial limitations and lack physical access. In addition, lack of information about nondaily hormonal contraceptives may also be a barrier for women considering contraception. The success of many family planning programs has been linked to removing administrative and medical barriers. Nondaily contraceptives can increase compliance. With oral contraceptives, missed pills are common and contribute to unintended pregnancies. Nondaily contraceptives offer dosing options that reduce the likelihood of missed dose.

Sayana®, revised formulation of depot medroxyprogesterone acetate (DMPA), is specifically formulated for subcutaneous administration. The contraceptive efficacy of Sayana® has been demonstrated in 2 large, multinational contraceptive trials, in which

Sayana® was highly effective and generally well tolerated. Zero pregnancies were reported in both trials (N=1,787) under perfect use conditions.

In addition to its high efficacy, Sayana® delivers a lower dose of medroxyprogesterone acetate than Depo-Provera Contraceptive Injection 150 mg/mL (medroxyprogesterone acetate injectable suspension, 150 mg/mL) and offers subcutaneous administration once every 3 months, thereby eliminating the need for the discipline of daily dosing.

Sayana® benefits from the established clinical history of Depo-Provera CI 150 mg for intramuscular administration, which contains the same active ingredient in a different formulation. Depo-Provera CI 150 mg has been available worldwide for decades and in the United States since 1992. Over 68 million women in over 114 countries worldwide have used Depo-Provera CI 150 mg, and the years of experience with Depo-Provera CI 150 mg worldwide provide a large body of long-term data regarding its safety and efficacy.

In December 2004, the FDA approved Sayana® for use as a contraception. Sayana® was approved in 48 countries over the world, among which 33 countries marketed Sayana® while 15 countries are under preparation for marketing.

Women who use Sayana® may lose significant bone mineral density. Bone loss is greater with increasing duration of use and may not be completely reversible. It is unknown if use of Sayana® during adolescence or early adulthood, a critical period of bone accretion, will reduce peak bone mass and increase the risk for osteoporotic fracture in later life.

Sayana® should be used long-term (eg, longer than 2 years) only if other methods of birth control are inadequate.

In South Korea, Sayana® was first approved as new medicine on 29 Jan 2013 by Ministry of Food and Drug Safety (MFDS). As required for any new medication approved by MFDS of Korea, Republic of, safety and effectiveness information of new medication should be provided at minimum 600 subjects administered in the setting of routine practice during the initial 6 years after the approval (29 Jan 2013 ~ 28 Jan 2019) through Post-Marketing Surveillance study.

However, as of 05 Mar 2018, MFDS approved 2 more years re-examination period extension due to low sales trend and enrollment difficulty after marketing. This study will be conducting by 28 Jan 2021 then safety and effectiveness information will be provided from these minimum 600 subjects.

## 6. RESEARCH QUESTION AND OBJECTIVES

This study is to describe the safety and effectiveness of Sayana® during the usual care setting.

The objective can be specified as below:

- To detect serious adverse events and adverse drug reactions.
- To detect unexpected adverse events and adverse drug reactions that are not included in precaution of local product document.

- To observe already known adverse drug reactions.
- To observe non-serious adverse drug reactions.
- To detect other information on safety and effectiveness.

## 7. RESEARCH METHODS

### 7.1. Study design

This study is an open-label, non-comparative, observational, non-interventional, prospective and multi-center study in which subjects administered Sayana® (administered as part of routine practice in Korean health care centers by accredited physicians) will be observed prospectively for a period of 6 months from the enrollment date. The visit schedule or interval will be decided by the investigator.

#### 7.1.1. Safety Endpoints

- Incidence of adverse events categorized according to physical organ and disease/symptom.

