## **9. ADVERSE EVENT REPORTING**

### **9.1. Requirements**

The table below summarizes the requirements for recording safety events on the case report form and for reporting safety events on the non-interventional study (NIS) adverse event monitoring (AEM) Report Form to Pfizer Safety. These requirements are delineated for three types of events: (1) serious adverse events (SAEs); (2) non-serious AEs (as applicable); and (3) scenarios involving drug exposure, including exposure during pregnancy, exposure during breast feeding, medication error, overdose, misuse, extravasation, and occupational exposure. These events are defined in the section “Definitions of safety events”.

Safety event	Recorded on the case report form	Reported on the NIS AEM Report Form to Pfizer Safety within 24 hours of awareness
SAE	All	All
Non-serious AE	All	None
Scenarios involving exposure to a drug under study, including exposure during pregnancy, exposure during breast feeding, medication error, overdose, misuse, extravasation; lack of efficacy; and occupational exposure	All (regardless of whether associated with an AE), except occupational exposure	All (regardless of whether associated with an AE)

For each AE, the investigator must pursue and obtain information adequate both to determine the outcome of the adverse event and to assess whether it meets the criteria for classification as a SAE (see section "Serious Adverse Events" below).

Safety events listed in the table above must be reported to Pfizer within 24 hours of awareness of the event by the investigator **regardless of whether the event is determined by the investigator to be related to a drug under study**. In particular, if the SAE is fatal or life-threatening, notification to Pfizer must be made immediately, irrespective of the extent of available event information. This timeframe also applies to additional new (follow-up) information on previously forwarded safety event reports. In the rare situation that the investigator does not become immediately aware of the occurrence of a safety event, the investigator must report the event within 24 hours after learning of it and document the time of his/her first awareness of the events.

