## **9.2. Definitions of Safety Events**

### **9.2.1. Adverse events**

An AE is any untoward medical occurrence in a patient administered a medicinal product. The event need not necessarily have a causal relationship with the product treatment or usage. Examples of adverse events include but are not limited to:

- Abnormal test findings (see below for circumstances in which an abnormal test finding constitutes an adverse event);
- Clinically significant symptoms and signs;
- Changes in physical examination findings;
- Hypersensitivity;
- Progression/worsening of underlying disease;
- Lack of efficacy;
- Drug abuse;
- Drug dependency.

Additionally, for medicinal products, they may include the signs or symptoms resulting from:

- Drug overdose;
- Drug withdrawal;
- Drug misuse;
- Off-label use;
- Drug interactions;
- Extravasation;

- Exposure during pregnancy;
- Exposure during breast feeding;
- Medication error;
- Occupational exposure.

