#### Lack of Efficacy

Reports of lack of efficacy to a Pfizer product are reported to Pfizer by the investigator, irrespective of the presence of an associated AE/SAE or the indication for use of the Pfizer product.

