6 ENDPOINTS AND COVARIATES

6.1 SAFETY ENDPOINTS

- All Adverse Events (AEs) Occurrence

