8.2.1.3 Adverse Events by Baseline Characteristics

The following will be presented for AEs, split by the baseline characteristics using the safety analysis set:

[figure not shown]
- The number of subjects to whom AE occurred and the number of AEs will be calculated.
- The proportion of subjects to whom AE occurred and its 95% confidence interval will be estimated and compared between subcategories of each baseline characteristic using a chi-square test or Fisher's exact test. When more than 20% of the expected frequency of the cell count is less than 5, Fisher's exact test will be used instead of the chi-square test.
- Adverse event presentations will be split by the following baseline characteristics: age, purpose of administration, medical history (past/present), concomitant medication, concomitant therapy, total number of injections of Sayana®, dose per injections of Sayana®, paediatric status, geriatric status, kidney disorder, liver disorder (see section 8.2.1.1).

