8.2.1.4 Adverse Events by Preferred Terms (AEs/ADRs/SAEs)

All AEs recorded in CRFs will be classified into the system organ class (SOC) and the terms of AE will be coded according to the classification of AEs in 'Precautions of Use' in the local product document of Sayana®/WHO-ART/MedDRA order. All AEs, except for those with causality of adverse event to the study drug classified as 'Unlikely', will be considered as AEs whose causal relationship to the study drug cannot be excluded (hereinafter "Adverse Drug Reaction (ADR)").

- The number and percentage of AE will be presented overall and by preferred term. This will be repeated by:

PFIZER CONFIDENTIAL

- severity
- action
- seriousness
- outcome
- causal relationship to Sayana®
- other causal relationship regarding occurred AE

- The number of subjects and the number of unexpected AE/ADR, SAE/Serious ADR (SADR), unexpected SAE/SADR, AE/ADR will be calculated according to the preferred terms. Also, the proportion of subjects to whom AE occurred will be estimated. In re-examination report, SAE/SADR and unexpected AE/unexpected ADR in accordance with preferred terms will be presented respectively according to the frequency categories of adverse events in the approved local label.
- The subjects with Serious AE, Unexpected AE, Unexpected Serious AE, AE of G eriatric, kidney disorder, liver disorder will be listed for safety analyses sets.
- For subjects excluded from the safety analysis set*, the number of subjects and the number of unexpected AE/ADR, SAE/Serious ADR (SADR), unexpected SAE/SADR, AE/ADR will be calculated according to the preferred terms. Also, the proportion of subjects to whom AE occurred will be estimated.

* Subjects excluded from safety analysis set: Subjects excluded from safety analysis set except for 'subjects who didn't receive Sayana®' and 'subjects for whom adverse event status (Adverse Events status is unknown or missing) could not be established'.

Note: Unexpected AEs/ADRs will be classified by medical review and with reference to the local product document. Terms already included in the local product document are classified as 'expected'. All other terms that are not included in the local product document will be classified as 'unexpected'. These can't be classified without the local product document.

- For subjects excluded from safety analysis set, Serious AE, unexpected AE, Unex pected Serious AE will be listed.

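### The AE and ADR proportions do not separate efficacy failure from side effects, so the comparison by purpose of administration can mix effectiveness with safety

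*Protocol*

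**What the plan says.** - **Endpoint.** Protocol 7.1.1 sets the safety endpoint as "Incidence of adverse events categorized according to physical organ and disease/symptom". SAP 6.1 states it as "All Adverse Events (AEs) Occurrence".
- **What counts as an AE.** The first list of examples in Protocol 9.2.1 includes "Progression/worsening of underlying disease" and "Lack of efficacy". A second list there covers signs or symptoms resulting from situations such as overdose. Lack of efficacy is in the first list, so it is named as an example in its own right.
- **What is counted.** SAP 8.2.1.2 summarises every AE reported after the start of administration. Neither document removes efficacy-failure terms or shows them separately.
- **ADR rule.** Under SAP 8.2.1.4, all AEs except those with causality rated Unlikely "will be considered as AEs whose causal relationship to the study drug cannot be excluded". Protocol 9.1.2 leaves causality to the investigator.
- **Comparison.** SAP 8.2.1.3 says "Adverse event presentations will be split by the following baseline characteristics: age, purpose of administration", followed by nine further characteristics. The proportion of subjects with any AE is compared between subcategories by chi-square or Fisher's exact test. SAP Appendix 1 sets a two-sided 5% level.
- **Reporting of lack of efficacy.** Protocol 9.1 puts it in a row of exposure scenarios to be recorded and reported "All (regardless of whether associated with an AE"). Protocol 9.2.3 adds: "Reports of lack of efficacy to a Pfizer product are reported to Pfizer by the investigator, irrespective of the presence of an associated AE/SAE", and extends this to any indication.

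**The concern.** Pain is the effectiveness outcome for endometriosis users (Protocol 7.1.2 and 7.7.1.3). If a site records worsening or insufficiently relieved pain as an AE, which Protocol 9.2.1 allows, that woman also counts in the safety outcome. For a contraception user, lack of efficacy means a pregnancy. The background in Protocol section 5 cites none among 1,787 women under perfect use.

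The same definition therefore gives the two groups unequal opportunity to meet it. A higher any-AE proportion in endometriosis users could reflect pain control rather than side effects, and the planned test could call it significant. The overall AE and ADR incidence would also move with the mix of indications and with how sites read Protocol 9.2.1.

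**Working it through.** The plan states no AE rate, indication mix or power for this comparison, so there is no figure to reproduce. The study size of 600 is a regulatory minimum (Protocol 7.5). What follows is an illustration.

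**Inputs**
- From the documents: N = 600, two-sided 5% level, chi-square test on the proportion with any AE.
- Assumed: true side-effect incidence p, equal in both groups; a split of 480 contraception and 120 endometriosis users; a fraction L of endometriosis users with lack of efficacy or worsening recorded as an AE, independently of other AEs; no such event in contraception users.

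**Endometriosis AE proportion** = p + (1 − p) × L. With p = 0.20:
- L = 1%: 0.20 + 0.80 × 0.01 = 20.8%
- L = 2%: 21.6%
- L = 5%: 24%
- L = 10%: 28%
- L = 20%: 36%

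The contraception proportion stays at 20%.

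**Probability that the test is significant.** This is the sum of the binomial probabilities of all outcomes for which the pooled chi-square statistic exceeds its 5% critical value.

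| Split | p | L = 1% | L = 2% | L = 5% | L = 10% | L = 20% |
|---|---|---|---|---|---|---|
| 480/120 | 20% | 6% | 7% | 17% | 47% | 95% |
| 480/120 | 10% | 6% | 10% | 30% | 75% | over 99% |
| 480/120 | 30% | 5% | 6% | 12% | 32% | 82% |
| 570/30 | 20% | 5% | 6% | 10% | 21% | 55% |

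With L = 0 every row is at about 5%. The smallest expected count is about 30 × 0.20 = 6, so the SAP's switch to Fisher's test would not normally apply in these rows.

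A normal-approximation calculation over endometriosis shares of 10% to 50% and p of 10% to 30% gives 4-11% at L = 2%, 9-39% at L = 5%, 21-88% at L = 10%, and 60% to over 99% at L = 20%.

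**Could contraceptive failure balance this?** The exact upper limit for 0 of 1,787 is 1 − 0.025^(1/1787) = 0.21%. At p = 20% that adds 0.80 × 0.21% = about 0.2 points to the contraception group. The source is perfect use, so routine use could be higher.

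**Overall AE incidence.** With 480/120, p = 20% and L = 10%: (480 × 0.20 + 120 × 0.28) / 600 = 129.6 / 600 = 21.6%, against 20% without these terms.

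**ADR proportion.** If a share u of these events is rated Unlikely, the excess in endometriosis users is (1 − p) × L × (1 − u), with p now the ADR incidence. At p = 20% and L = 10% this is 8 points for u = 0, 4 points for u = 0.5 and 0 for u = 1.

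**The case against.** The strongest reply is that the documents do not force any of this, and much of that reply stands.

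- **Automatic AE or ADR status.** A reader might infer that every unrelieved pain becomes an AE and an ADR, so that the comparison is biased. The documents do not support this. Unchanged pain is not worsening, nothing states when insufficient relief counts as lack of efficacy, and ADR status depends on the investigator's causality rating.
- **Double counting of the VAS.** No rule turns a VAS score into an AE. Effectiveness is analysed as mean change, without a failure threshold. The overlap arises only where an investigator records the pain as an AE.
- **Different definitions by group.** One definition covers both groups. Protocol 9.2.1 speaks of underlying disease, which a contraception user may also have, and the lack-of-efficacy reporting rule covers any indication. Only the opportunity differs.
- **A contradiction within the protocol.** Sections 9.1 and 9.2.3 are recording and reporting rules, and they can coexist with 9.2.1. Saying whether lack of efficacy alone is an AE would be a useful clarification, but this is not an established conflict.
- **Little inferential weight.** The study is non-comparative, Protocol 7.7.2 says no hypotheses will be tested, and this is one of many unadjusted splits. Women with endometriosis also differ in other ways. This limits the harm, but SAP 8.2.1.3 still plans the test and Appendix 1 still declares significance.
- **Preferred-term tables.** Efficacy-failure terms coded separately would have their own rows under SAP 8.2.1.4, and some cases might appear in the listing of unexpected AEs. The tables do not show which subjects had only such an event, so the any-AE proportion without them cannot be recovered.

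**Conclusion.** The concern holds as a possibility that the plan leaves open. Followed as written, the plan lets efficacy failure into the AE proportion, and into the ADR proportion unless causality is rated Unlikely. The comparison by purpose of administration can then mix effectiveness with safety. The likely direction is upward for endometriosis users, because contraception users have little chance of a matching event.

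The size is unknown. It depends on the indication mix, the true AE incidence and above all the recording rate, none of which the documents give. Across the assumed ranges the effect runs from negligible, at 1-2% recording, to dominant, at 20% recording with a sizeable endometriosis group. The documents do not show that the comparison is biased. The case for a change is that the remedy is cheap and uses data already collected.

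**What to change.** In SAP 8.2.1.2 to 8.2.1.4:
- show lack of efficacy and worsening of the treated endometriosis pain on their own line;
- report AE and ADR incidence with and without these terms, on the same denominators;
- present the purpose-of-administration comparison both ways, and read the version without them as the side-effect comparison.

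CRF recording and 24-hour reporting stay as they are.

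The cost is SAP wording and one extra row in existing tables, with no new data. The drawback is that the version without these terms could leave out a worsening that the drug caused, which is why both versions are shown.
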